## 5.2. Overall Rationale

The clinical development program for daclizumab to date has demonstrated that the therapy is highly efficacious in the treatment of RMS, is well tolerated, has a safety profile that is manageable with appropriate monitoring and routine clinical care, and offers convenient once-monthly self-administered SC injection dosing [Kappos 2015c; Selmaj 2013]. In the 2 to 3 year, comparator-controlled, phase 3 DECIDE trial, daclizumab (150 mg) treatment resulted in several statistically significant effects compared to once-weekly IM IFN $\beta$ -1a including reduction in ARR by 45%, reduction in 24-week confirmed disability progression by 27%, and reduction in the formation of MRI lesions by 65% (Gd+), 54% (new/newly enlarging T2-hyperintense), and 52% (new T1-hypointense lesions) [Kappos 2015a; Kappos 2015b]. Additional findings from DECIDE indicated that daclizumab resulted in clinically meaningful cognitive improvement (as assessed by the SDMT) compared to IM IFN $\beta$ -1a, and fewer subjects receiving daclizumab experienced cognitive decline [Benedict 2015].

From a safety perspective, clinical data to date indicate no risk of opportunistic infections with daclizumab and, importantly, no risk of PML. The risks associated with daclizumab (e.g., infections, rash, dermatitis, hepatic enzyme abnormalities) have been shown to be manageable with standard monitoring and medical interventions [Gold 2013; Kappos 2015a; Kappos 2015c].

Although evidence demonstrates that natalizumab is a highly effective treatment for RMS, a number of patients who are effectively responding to therapy ultimately discontinue treatment due to concerns regarding the risk of PML or the occurrence of AEs [Butzkueven 2014; Polman 2006]. Multiple DMTs have been investigated as post-natalizumab treatment options, including fingolimod, DMF, IFN $\beta$ , GA, and pulsed steroids, but the results have been mixed, with some patients exhibiting MS disease activity despite alternative treatment [Centonze 2012; Clerico 2014; Cohan 2015; Cohen 2014; Faissner 2015; Fox 2014; Kappos 2015b; Rossi 2013]. In

CONFIDENTIAL

The information contained herein may not be used, disclosed, or published without the written consent of Biogen MA Inc.

multiple studies investigating the efficacy of fingolimod following discontinuation of natalizumab, upwards of 25% of subjects experienced a clinical relapse within the first 6 months of starting fingolimod [Comi 2015; Comi 2013; Kappos 2015c]. In a retrospective, observational study investigating the efficacy of DMF following discontinuation of natalizumab (STRATEGY), overall ARR increased from 0.114 on natalizumab to 0.248 after 1 year of DMF treatment [Cohan 2015]. Therefore, there remains an unmet medical need for new alternative high-efficacy treatment options for the often difficult to treat population of RMS patients who find it necessary to discontinue a therapy that otherwise may be effectively managing their disease.

Considering that daclizumab is a highly efficacious treatment for RMS with a manageable safety profile and no increased risk of PML to date, it could be a compelling option for patients switching off natalizumab. Therefore, the SUSTAIN study aims to establish whether daclizumab is a suitable DMT for RMS patients discontinuing natalizumab.

### 5.2.1. Rationale for Duration between Therapies

As part of the study design, subjects must receive their first dose of daclizumab at 28 (+ 3) days following discontinuation of natalizumab. The rationale for this requirement is to minimize the washout period between daclizumab and natalizumab. Clinical research studies in patients switching from natalizumab to an alternative treatment option have shown that disease activity can occur within the first 6 months of discontinuing natalizumab. However, in several of these studies, the risk of disease recurrence was shown to be mitigated with a shorter washout period between treatments [Cohan 2015; Kappos 2015c]. In a randomized trial evaluating the effects of natalizumab treatment interruption (RESTORE), it was shown that natalizumab concentrations reach undetectable levels 8 weeks after discontinuation [Cree 2013]. Pharmacodynamic (PD) studies with daclizumab demonstrated increases in CD56bright NK cells and serum IL-2 levels within the first 4 weeks of treatment [Amaravadi 2015] and effects on disease activity, as evidenced by reductions in Gd+ lesion activity, were apparent within 8 to 12 weeks (SELECT; Biogen, data on file). These data indicate that a 28-day gap between the discontinuation of natalizumab and the initiation of daclizumab would maximize the PD overlap of these 2 therapies and thus minimize the amount of time patients are not protected by a highly efficacious therapy.

With respect to the time interval between natalizumab discontinuation and daclizumab initiation, it is also important to consider how these therapies are thought to function in the body and the possibility of additive immunosuppressive effects. Daclizumab and natalizumab impact the pathophysiology of MS in distinct and reversible ways. Daclizumab is a humanized monoclonal antibody that targets CD25 and reversibly modulates IL-2 signaling. These effects result in 1) selective antagonism of pro-inflammatory activated T cell function and 2) expansion of immunoregulatory CD56bright NK cells [Bielekova 2013; Pfender and Martin 2014; Wiendl and Gross 2013]. Natalizumab is a selective adhesion molecule inhibitor that binds to the  $\alpha$ 4-subunit of human integrins, disrupting their interaction with ligands such as vascular cell adhesion molecule-1. This action reduces the ability of immune cells to cross the blood-brain barrier and enter the CNS [Polman 2006; Tysabri® Prescribing Information 2013/SmPC]. Presently, no biological evidence suggests a risk of AEs resulting from the additive biological effects of these 2 therapies; the SUSTAIN study is expected to address this paucity of data. Ultimately, a

CONFIDENTIAL

The information contained herein may not be used, disclosed, or published without the written consent of  
Biogen MA Inc.

natalizumab washout period of 28 days is thought to represent an effective balance between efficacy and safety, and findings from this study are anticipated to help address the important unmet medical need of successful treatment post-natalizumab.

### **5.2.2. Rationale for Dose and Schedule Selection**

Single-use, disposable pre-filled pens, also known as autoinjectors, will be provided to simplify the injection process and thereby reduce the burden of administering a long-term therapy such as daclizumab in the clinic or at home. The dose and frequency of daclizumab used in this study is the same used in other phase 3 studies of daclizumab (DECIDE, Study 205MS301; OBSERVE, Study 205MS302; EXTEND, Study 205MS303).

CONFIDENTIAL

The information contained herein may not be used, disclosed, or published without the written consent of  
Biogen MA Inc.

## 6. STUDY OBJECTIVES AND ENDPOINTS

### 6.1. Objectives

#### 6.1.1. Primary Objective and Endpoints

The primary objective of the study is to evaluate the effects of treatment with daclizumab on the proportion of subjects relapse-free at 6 months in RRMS subjects, who switched from treatment with natalizumab to daclizumab due to safety concerns.

The primary endpoint is the proportion of subjects relapse-free at Month 6 in RRMS subjects treated with daclizumab, who switched from treatment with natalizumab.

See Section 11 for the definition of relapse.

#### 6.1.2. Secondary Objectives and Endpoints

The secondary objectives of this study in this study population are to evaluate the effects of daclizumab on the following:

- MS relapse activity including the ARR and the proportion of subjects experiencing relapses requiring hospitalization and/or steroid treatment.
- MS-related outcomes measured using MRI.
- Safety and tolerability in subjects previously treated with natalizumab.

The secondary endpoints that relate to these objectives are the following:

- The proportion of subjects relapse-free at Month 12.
- The proportion of subjects experiencing relapse requiring hospitalization and/or steroid treatment at Month 12.
- The ARR at Month 12.
- The number of new Gd+ enhanced and T1 hypointense lesions at Month 6 and Month 12 on MRI.
- The number of new or newly enlarged T2 hyperintense lesions at Month 6 and Month 12 on MRI.
- The permanent discontinuation rate of daclizumab at Month 12.
- The incidence of AEs and SAEs including clinically relevant shifts in clinical laboratory assessments.

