## 4.2. Schedule of Assessments

The schedule of assessments is presented in [Table 1](#). Assessment time points include an enrollment visit, a baseline visit, and follow-up visits at Months 1, 3, 4, 6, 9 and 12. An additional safety assessment will be performed remotely 4 months after the last study treatment dose. Subjects who discontinue treatment early will still be evaluated during the safety follow-up visit (i.e., 4 months after treatment and study discontinuation). Subjects having tentative disability progression identified near the end of the core study (e.g., Month 12) will attend additional follow-up visits 12 and 24 weeks later to confirm progression.

Magnetic resonance imaging (MRI) scans will be performed at the enrollment visit (no later than 7 days prior to the first dose of daclizumab), and at Months 1, 4, 6 and 12. MRI scans will be performed under the supervision of a trained radiologist. Ad-hoc MRI scans may be performed as needed, such as in the event of a MS relapse, in order to rule out a progressive multifocal leukoencephalopathy (PML) diagnosis.

Blood chemistry and hematology assessments will be performed at baseline and at Months 1, 3, 6, 9 and 12. Hematology assessments will include a complete blood count (CBC). Liver function tests (LFT) [alanine transaminase (ALT)/ aspartate transaminase (AST)] will be done at enrollment and monthly visits. Bilirubin testing must be done together with the first AST/ALT test at the enrollment visit. Bilirubin testing must also be done if ALT/SGPT (serum glutamic pyruvate transaminase), or AST/SGOT (serum glutamic oxaloacetic transaminase)  $>3*$ upper limit of normal (ULN), since treatment must be permanently discontinued with the concomitant elevation of total bilirubin  $>2*ULN$ .

At the end of the study, liver monitoring will be done per routine clinical practice.

A safety follow-up visit at 4 months after the last dose of daclizumab provided by the study will be conducted remotely to evaluate potential delayed safety outcomes. The assessments during the additional safety follow-up period will include all safety endpoints described in [Table 1](#). Liver function tests (LFT) will be performed only if the subject is continuing daclizumab or if the subject is within 4 months since study treatment discontinuation, and monitoring is deemed appropriate by the Investigator.

CONFIDENTIAL

The information contained herein may not be used, disclosed, or published without the written consent of  

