### **13.5. Secondary Endpoints Analysis**

#### **13.5.1. Efficacy Analysis**

The proportion of subjects relapse-free at Month 12 will be estimated using Kaplan-Meier approach. This will be calculated as 1 minus the proportion of subjects with relapses at Month 12. For the Kaplan Meier approach, the time to relapse is the number of days from the date of the first dose of daclizumab to the date of first relapse, or end of study, whichever comes first. The Cox proportional hazard model will be used to estimate the hazard ratio of relapses between subject subgroups of interest.

The proportion of subjects relapse-free 12 months before and 12 months after switching to daclizumab will be compared using McNemar's Test for subjects who had relapse information available at the above time points (study completers).

The proportion of subjects experiencing relapse requiring hospitalization and/or steroid treatment at Month 12 will be estimated using the Kaplan-Meier approach. For the Kaplan-Meier approach, the time to relapse requiring hospitalization and/or steroid treatment will be the number of days from the date of the first dose of daclizumab to the date of first relapse requiring hospitalization and/or steroids treatment, or end of study, whichever comes first. A Cox proportional hazard model will be used to estimate the hazard ratio of relapses requiring hospitalization and/or steroids treatment between subject subgroups of interest.

The ARR with 95% CI at Month 12 (calculated as the total number of relapses divided by the total number of person-years in the study at the end of Month 12 for each subject) will be estimated using a negative binomial model. If the data are under-dispersed or if the negative binomial regression does not converge, a Poisson regression model with the same covariates will be used instead. Given that subjects may have more than 1 relapse in 12 months, the number of relapses will be summarized both as a continuous variable and as a categorical variable.

The number of new Gd+ enhanced and T1 hypointense lesions at Month 6 and Month 12 and the number of new or newly enlarged T2 hyperintense lesions at Month 6 and Month 12 when compared with baseline will be summarized both as continuous variables and as categorical variables. A negative binomial model adjusting for the corresponding baseline MRI lesion counts will be used to estimate the adjusted mean and lesion mean ratio between subject subgroups of interest.

CONFIDENTIAL

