5.2.3 Analysis for MRI endpoints

MRI is measured from all subjects in this study.. Records up to 28 days after the first dose can be used as baseline assessments. If there are multiple records, then the one closest to the first dosing date will be selected; if tied, then the record prior to the first dose will be defined as baseline.

At each visit where MRI data is available, the number of Gd+ lesions , the number of T1 hypointense lesions, and the number of new or newly enlarged T2 hyperintense lesions, will be summarized both as continuous variables and as categorical variables (number of lesions being 0, 1, 2, 3 and ≥ 4).

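### The Gd+ endpoint names only Months 6 and 12, and the by-visit tables for Months 1 and 4 cannot show how many subjects had any new Gd+ lesion after the switch

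*Protocol*

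**What the plan says.** Protocol 6.1.2 defines the endpoint as "The number of new Gd+ enhanced and T1 hypointense lesions at Month 6 and Month 12 on MRI". Protocol 13.5.1 analyses the same two time points, and SAP 1.2 repeats them.

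Protocol 4.2 schedules MRI at enrollment "and at Months 1, 4, 6 and 12". Section 11.1 requires each protocol scan with and without gadolinium, and sections 11.3.3 and 16.1.4 provide for central reading.

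On timing, Protocol 5.2.1 says that "it was shown that natalizumab concentrations reach undetectable levels 8 weeks after discontinuation". It puts daclizumab's effect on Gd+ lesions at 8 to 12 weeks, and it notes that "disease activity can occur within the first 6 months of discontinuing natalizumab". The first daclizumab dose comes 28 (+3) days after the last natalizumab infusion.

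For T2, Protocol 13.5.1 takes "the number of new or newly enlarged T2 hyperintense lesions at Month 6 and Month 12 when compared with baseline".

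SAP 5.2.3 is broader than the endpoint: "At each visit where MRI data is available, the number of Gd+ lesions" is summarised as a continuous variable and in categories 0, 1, 2, 3 and 4 or more. It contains no negative binomial MRI model. On baseline it says: "Records up to 28 days after the first dose can be used as baseline assessments". The record closest to first dose is chosen, and a tie goes to the pre-dose record.

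**The concern.** The MRI objective is to describe disease activity after the switch. Exclusion criterion 15 removes anyone with Gd+ or new T2 activity in the 6 months before screening, so a new Gd+ lesion after the switch is returning activity. The natural reader's question is how many subjects had any by Month 6 and by Month 12.

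The named endpoint cannot answer this. A lesion that enhances only at Month 1 or Month 4 does not enter it. A subject scanned at those visits who has no Month 6 scan contributes nothing, and the study was stopped with limited follow-up. The by-visit tables show the early counts but do not link visits within a subject.

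**Working it through.** **1. The plan's own figures.** Neither document gives a figure for the Gd+ endpoint. The only sizing figure concerns the relapse-free proportion (Protocol 13.1). The evaluable number is 100 × (1 − 0.10) = 90. The half-width 1.96 × √(p(1 − p)/90) is 8.26 points at p = 0.80 and 6.71 points at p = 0.88. These reproduce the stated 8.3% and 6.7% but do not bear on Gd+.

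**2. The least-protected interval (Protocol 5.2.1).**
- Natalizumab undetectable: 56 days after the last infusion − 28 days = study day 28, about Week 4.
- Daclizumab effect on Gd+ apparent: study Weeks 8 to 12.
- The interval is therefore about Weeks 4 to 12. The Month 6 scan is at about Week 26.1, which is 26.1 − 12 = 14.1 weeks after it ends.

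**3. Why by-visit tables are not enough.** This step needs no model of lesion rates. Suppose 3 of 30 subjects have a Gd+ lesion at each of Months 1, 4 and 6, with all 30 scanned each time. If they are the same 3 subjects, 10% had any lesion by Month 6. If no subject repeats, 9 of 30 (30%) did. The tables are identical in both cases.

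**4. Size under stated assumptions.** The documents give no per-scan rate for this population. I take 0.2 or 0.5 new lesions per scan (0.5 is the 24-week daclizumab mean quoted for DECIDE in Protocol 5.1.4). A gamma subject effect with dispersion α from 1 to 4 is shared across a subject's scans, so scans are correlated. Over k scans, P(any) = 1 − (1 + αkμ)^(−1/α).

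| μ | α | Month 6 | Months 1, 4, 6 | Ratio | Months 6, 12 | All four | Ratio |
|---|---|---|---|---|---|---|---|
| 0.2 | 1 | 16.7% | 37.5% | 0.44 | 28.6% | 44.4% | 0.64 |
| 0.2 | 4 | 13.7% | 26.4% | 0.52 | 21.2% | 30.1% | 0.71 |
| 0.5 | 1 | 33.3% | 60.0% | 0.56 | 50.0% | 66.7% | 0.75 |
| 0.5 | 4 | 24.0% | 38.5% | 0.62 | 33.1% | 42.3% | 0.78 |

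The table holds the rate constant over visits. For Months 6 and 12 against all four scans, other assumptions widen the range. Per-scan probabilities of 0.05, 0.25, 0.05 and 0.05 at Months 1, 4, 6 and 12 give 0.27. A late-peaked profile of 0.02, 0.05, 0.15 and 0.15 gives 0.85.

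**5. What the early scans can see.** Assume enhancement lasts 6 to 8 weeks (not in the documents), with Months 1, 4 and 6 at Weeks 4.35, 17.4 and 26.1. Of lesions formed evenly over Weeks 4 to 12:
- Month 6 looks back at most to Week 18.1 and sees none.
- Months 1 and 4 see (0.35 + 0.6)/8 = 12% at 6 weeks' duration and (0.35 + 2.6)/8 = 37% at 8 weeks.

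**6. The baseline window.** Take Month 1 as day 28 to 30. With a visit window of ±4 days and MRI allowed up to 4 days earlier (Protocol Table 1 and its note 2), the scan can fall as early as day 20 to 22. The enrollment scan lies between 31 and 7 days before first dose. A Month 1 scan on day 20 therefore becomes baseline if the enrollment scan was 21 or more days before dosing. One on day 28 does so if it was 29 or more days before. SAP 4.3 defines baseline generally as on or before first dose, so 5.2.3 departs from the SAP's own rule.

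**The case against.** A reader might infer that the Month 1 and Month 4 scans are ignored. They are not. SAP 5.2.3 reports them, including the zero category, so the share with any Gd+ lesion at each visit can be read off. Protocol T2 counts against baseline also accumulate activity between scans. Both points stand, and they confine the gap to the cumulative, per-subject view.

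A reader might also infer that the share of subjects with returning activity is roughly halved. The documents do not support that as a finding. No rate is given, the endpoint is a lesion count rather than a share of subjects, and for Months 6 and 12 against all four scans the same model gives 0.64 to 0.78.

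Nor does the calculation show bias. With a constant rate, the Month 6 count estimates the per-scan rate correctly, and P(any) rises simply because there are more scans. A favourable bias would need an early peak, for which the documents give no figure. The protocol's wider risk period of 6 months after stopping natalizumab runs to about study Month 5. Under the 6-to-8-week assumption, the Month 6 scan covers the end of that period.

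Other limits are fair. Step 5 leaves 63% to 88% of lesions from Weeks 4 to 12 unseen even with the early scans. The protocol's negative binomial MRI model is not in the SAP, so gains in model precision are beside the point. Single-visit counts match the way DECIDE is quoted. The exploratory endpoints are redacted, so a cumulative measure may exist there. None of this removes the value of linking scans already taken.

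**Conclusion.** The point holds in a limited form. The named Gd+ endpoint uses two of four post-baseline scans and omits the two nearest the interval that Protocol 5.2.1 implies is least protected. No readable part of either document gives a per-subject cumulative Gd+ summary. That gap is structural and does not depend on any assumed rate.

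Its size does. Under constant-rate gamma-Poisson assumptions, Month 6 alone shows about 0.44 to 0.62 of the share over Months 1, 4 and 6, and Months 6 and 12 show about 0.64 to 0.78 of the share over all four scans. If the rate varies by visit, the second ratio could lie anywhere from about 0.27 to 0.85.

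The baseline rule is a second, smaller weakness. It applies only when the enrollment scan is about three weeks old or more and the Month 1 scan is no later than day 28, but then returning activity can be counted as baseline.

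**What to change.** Change SAP 5.2.3 as follows:
- Add a per-subject cumulative summary of new Gd+ lesions over the scheduled scans through Month 6 (Months 1, 4, 6) and through Month 12 (Months 1, 4, 6, 12). The by-visit text says Gd+ lesions without the word new, so state that a lesion still enhancing on a later scan counts once.
- Report total new lesions per scan performed.
- Report the proportion with any new Gd+ lesion, with an exact 95% CI, among subjects with at least one post-baseline scan. State how many scans each subject contributed, because early termination makes the numbers unequal and nothing is imputed.
- Do not let a Month 1 scan serve as baseline when a pre-dose scan exists. This restores the rule in SAP 4.3.
- Keep the by-visit tables.

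The cost is some SAP wording and one descriptive table from scans already scheduled and centrally read. The Gd+ figures will look less favourable, since a cumulative share cannot be lower than a single-visit share in the same subjects. They will also be imprecise with about 30 subjects: the exact 95% CI is 2.1% to 26.5% for 3 of 30 and 14.7% to 49.4% for 9 of 30. The table should be labelled descriptive.

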#### 6.1.3. Exploratory Objectives and Endpoints

The exploratory objectives of this study in this study population are to evaluate the effects of daclizumab on:

- [REDACTED]

CONFIDENTIAL

The information contained herein may not be used, disclosed, or published without the written consent of Biogen MA Inc.

- [REDACTED]
- [REDACTED]
- [REDACTED]

The endpoints associated with the exploratory objectives are the following:

- [REDACTED]
- [REDACTED]
- [REDACTED]
- [REDACTED]
- [REDACTED]
- [REDACTED]
- [REDACTED]
- [REDACTED]
- [REDACTED]
- [REDACTED]

CONFIDENTIAL

The information contained herein may not be used, disclosed, or published without the written consent of Biogen MA Inc.

## **7. STUDY DESIGN**

### **7.1. Study Overview**

This is a multicenter, open-label study of daclizumab monotherapy in subjects with RRMS who were previously treated with natalizumab for at least 12 months. Approximately 100 subjects will be enrolled from approximately 40 sites in the US and rest of world over a 12-month period.

Following consent and evaluation of eligibility, subjects will discontinue natalizumab and commence treatment with daclizumab. Subjects will initiate treatment with daclizumab at 28 (+3) days following the last infusion of natalizumab. A detailed description of study assessments is provided in Section 9.2.

The assessment schematic provides an overview of the study assessment schedule (Table 1). Assessments will be performed at enrollment, baseline, Month 1, Month 3, Month 4, Month 6, Month 9 and Month 12. The additional safety follow-up visit will be conducted remotely.

